3. GENERAL ANALYSIS AND REPORTING CONVENTIONS

All efficacy analyses will use a two-sided alpha = 0.05 test unless otherwise stated. P-values will be rounded to four decimal places. If a p-value is less than 0.0001, it will be reported as “<0.0001.”

Continuous data will be described using descriptive statistics: sample size, mean, SD, median, Q1 and Q3, minimum, and maximum. Minimums and maximums will be reported with the same precision as the raw values; medians, Q1, Q3 and means will show precision to one decimal place greater than the raw values; SDs will show precision to two decimal places greater than the raw values. For example, if height is recorded in whole centimeters, min and max will be displayed as whole centimeters, means will be shown as xxx.x and SD will be shown as xxx.xx. Data will be displayed in all listings sorted by treatment group and subject identification number. Subjects will be identified in the listings by the subject identification number concatenated with the investigator number.

When count data are presented, the percentage will be suppressed when the count is zero in order to draw attention to the non-zero counts. The denominator for all percentages will be the number of subjects with non-missing data in that treatment group within the population of interest.

For the duration of leg pain covariate, if partial dates are provided, then missing dates will be imputed as the 15th for a missing day and July for a missing month, consistent with prior protocols.

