7.3.3.3 Other Secondary

All endpoints, including the primary and key secondary endpoints, will be summarized by treatment group and by time point. The differences of other secondary endpoints between the SI-6603 and control groups will be analyzed at each time point they are collected as below.

- A similar longitudinal analysis model will be used as described in the primary efficacy analysis for the analysis of change from baseline in pain intensity scores, function scores, QOL scores, and volumes (intervertebral disc and herniation), by including the corresponding baseline value as the fixed effect instead of the baseline worst leg pain score.
- Percentage change from baseline in intervertebral disc and herniation volumes will be summarized in a line graph with error bars.
- Neurologic status as determined by neurological examinations will be compared between treatments with a difference in proportions Z test. In the case of low counts (<5 expected in a cell), a Fisher's exact test will be used. Outcomes will include SLR test, sensation, muscle strength, and deep tendon reflex. Counts and percentages in each category will be presented along with 95% confidence intervals, the difference in the percentages and its 95% Wald CI. Percentages will be reported out of non-missing values.
- For the global assessments of PGIC score and CGIC score, responder analysis with the two best categories as "responder" will be compared between treatments with a difference in proportions Z test. In the case of low counts (<5 expected in a cell), a Fisher's exact test will be used. Counts and percentages in each category for the PGIC and CGIC will be presented as well as the responder/non-responder counts and percentages along with 95% confidence intervals, the difference in the percentages of responders and its 95% Wald CI. Subjects with missing values will be considered non-responders.
- Scores on the WPAI will be analyzed with the analysis of covariance model including the baseline value and duration of leg pain as covariates.
- The incidence of rescue medication use will be compared between treatments with a difference in proportions Z test. In the case of low counts (<5 expected in a cell), a Fisher's exact test will be used. The amount of rescue medication use will be analyzed with the Wilcoxon rank sum test.

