- Cumulative distribution of percentage change from baseline in worst leg pain and ODI will be generated, and differences between the SI-6603 and control groups in the percentages of subjects experiencing a $\geq 30\%$ and $\geq 50\%$ improvement in worst leg pain score will be compared between treatments with a difference in proportions Z test. In the case of low counts (< 5 expected in a cell), a Fisher's exact test will be used. Additionally, the difference in the percentages of responders and its 95% Wald CI will be reported. Subjects with missing values will be considered non-responders/not having improvement.
- For the analysis of the percentages of responders by composite definition, differences between the SI-6603 and control groups in the percentages of positive responders will be compared between treatments with a difference in proportions Z test. In the case of low counts (< 5 expected in a cell), a Fisher's exact test will be used. Counts and percentages of responders will be presented along with 95% confidence intervals, the difference in the percentages and its 95% Wald CI. See section [7.3.3.4](#) for the definition of composite responder.
- The number of subjects with recurrence of LDH, percentages and differences between the SI-6603 and control groups in the percentages will be reported. See section [7.3.3.5](#) for the definition of recurrence of LDH.
- Time to post-treatment surgery for LDH will be evaluated by survival analysis using Kaplan-Meier methodology and the log-rank test. Counts and percentages of subjects with post-treatment surgery will be reported as well as medians and quartiles of the time to surgery (if they are defined). Additionally, the number and percentage of subjects with post-treatment surgery for LDH will be reported and compared between treatment groups with a Fisher's exact test. The difference in the percentages of responders and its 95% Wald CI will also be reported.
- Time to post-treatment surgery for LDH will be summarized in a Kaplan-Meier plot.

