8.2 Adverse Events

All AEs will be coded using Medical Dictionary for Regulatory Activities (MedDRA) using the current version at the time coding is first initiated. TEAEs will be defined as any AEs that were recorded during or following the investigational product injection. Significant TEAEs will include TEAEs that result in study discontinuation. TEAEs of special interest will include TEAEs associated with hypersensitivity, imaging findings, leg pain, and back pain.

An overall display will show the number and percentage of subjects (with exact 95% CI) with TEAEs or treatment-related TEAEs that fall into the following categories: any TEAE; TEAE leading to death; serious TEAE; significant TEAE; TEAE associated with hypersensitivity; TEAE associated with imaging findings; TEAE associated with leg pain; TEAE associated with back pain. TEAEs related to study procedure will be summarized. In addition the number of subjects with TEAEs or treatment-related TEAEs will be summarized by the following:

Relationship to Study Drug	Severity	Time of First Occurrence (after injection)
Related AEs	Mild AEs	≤ 1 day
Not Related AEs	Moderate AEs	2 – 7 days
	Severe AEs	8 days – 13 weeks
		>13 weeks

Subjects experiencing AEs in more than one category will be counted in the most severe or most related group.

Detailed listings of all AEs will include severity and relationship to treatment, as well as action taken, subject outcome, and whether the AE is diagnosed or suspected COVID-19. Separate listings will be provided of subjects who experience serious TEAEs, significant TEAEs, and special interest TEAEs. Additionally, any information recorded for AEs of diagnosed or suspected COVID-19 regarding descriptions of signs/symptoms, treatments, diagnostic test results, and the resolution will be presented in a listing.

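### SAP 7.3.3.3 keeps a Wald interval for differences in proportions in sparse tables tested with Fisher's exact test; a Newcombe interval should replace it there

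*SAP*

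**What the plan says.** Two rules in SAP 7.3.3.3 matter, and they differ.

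- **Post-treatment surgery for herniation.** Besides the Kaplan-Meier and log-rank analysis, "the number and percentage of subjects with post-treatment surgery for LDH will be reported and compared between treatment groups with a" Fisher's exact test. No Z test comes first and there is no trigger. The interval is Wald: "The difference in the percentages of responders and its 95% Wald CI will also be reported".
- **Other binary endpoints.** Neurologic status, PGIC/CGIC response, 30%/50% improvement in worst leg pain and composite response start with a Z test for the difference. Fisher's test replaces it under a clause that opens "In the case of low counts (<5 expected in a cell". The interval does not change with the test. For neurologic status: "Counts and percentages in each category will be presented along with 95% confidence intervals, the difference in the percentages and its 95% Wald CI". For 30%/50% improvement: "Additionally, the difference in the percentages of responders and its 95% Wald CI will be reported". For composite response: "Counts and percentages of responders will be presented along with 95% confidence intervals, the difference in the percentages and its 95% Wald CI". The PGIC/CGIC item is worded to the same effect.

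Rescue medication use has the switch to Fisher's test but no interval, and recurrence of herniation has neither test nor interval. Exact limits are specified in SAP 8.2, for adverse event incidences within one group: "An overall display will show the number and percentage of subjects (with exact 95% CI"). Neither document gives a score or exact interval for a difference between groups.

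**The concern.** The Wald interval and the Z test both rest on a normal approximation to the difference in proportions. For the switching endpoints, the SAP drops that approximation for the p-value when counts are low and keeps it for the interval printed beside the p-value. For surgery it never uses the approximation for the test, yet relies on it for the interval.

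The weakness is well defined. An arm with no events contributes zero estimated variance, so the interval is too short when one arm is at or near zero and has no width when both are. The printed limits could then cover well below 95%, or exclude zero beside a clearly non-significant p-value. Surgery is where this matters most: it is a listed efficacy endpoint (Protocol 8.1.3, SAP 7.2), and Protocol 1.1 presents chemonucleolysis as an alternative to surgery.

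**Working it through.** **Inputs.** n = 160 per arm (SAP 2.6). Level: "All efficacy analyses will use a two-sided alpha = 0.05 test unless otherwise stated" (SAP 3), so z = 1.96. Event rates are assumptions from 0% to 10%, because the documents state none for surgery or another rare outcome. Everyone is assumed to be evaluable.

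**The plan's own figure.** The documents give no coverage figure to reproduce, only the sample size. With a 12 mm difference and SD 30 mm, n = 2 × (1.960 + 1.282)² × 30²/12² = 131.4, so 132 per arm; 132/0.85 = 155.3, so 156 (157 with the noncentral t). The planned 160 is consistent with that.

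**When the low-count rule applies.** With equal arms the smaller expected count is (total events)/2. It is below 5 when there are fewer than 10 events, or fewer than 10 non-events, among 320 subjects (10/320 = 3.1%).

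**4 vs 0 events.**
- Wald: p₁ − p₂ ± 1.96 √[p₁(1−p₁)/n + p₂(1−p₂)/n] = 0.025 ± 1.96 × √(0.025 × 0.975/160) = 0.025 ± 0.0242, or 0.08 to 4.92 points.
- Fisher, two-sided: 2 × (160·159·158·157)/(320·319·318·317) = 0.123.
- Newcombe: the Wilson limits are 0.98% to 6.25% for 4/160 and 0% to 2.34% for 0/160. Lower limit: 2.50 − √[(2.50 − 0.98)² + 2.34²] = −0.30. Upper limit: 2.50 + (6.25 − 2.50) = 6.25.

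**0 vs 0 events.** Wald gives 0 to 0; Newcombe gives −2.34 to +2.34 points. At a true rate of 0.5% in both arms, this table has probability 0.995³²⁰ = 20%.

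**Why coverage falls: 0% vs 2%.** The true difference is 2 points and only one arm has events. The Wald interval misses with 0 events (0 to 0), with 1 event (−0.60 to 1.85) and with 9 or more (lower limit 2.05 at 9). The binomial probabilities are 0.0395 + 0.1289 + 0.0052 = 0.1736, so coverage is about 82.6–82.7%.

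**Exact coverage, summed over the joint binomial distribution.**

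| Assumed true rates | Wald | Newcombe |
|---|---|---|
| 0% vs 1% | 79.9% | 99.9% |
| 0% vs 2% | 82.7% | 99.5% |
| 0% vs 3% | 85.8% | 98.3% |
| 0.5% vs 1% | 86.9% | 99.6% |
| 0.5% vs 2% | 92.8% | 98.4% |
| 1% vs 4% | 92.8% | 96.6% |
| 2% vs 5% | 93.8% | 96.2% |
| 5% vs 10% | 95.0% | 95.5% |
| 0.5% in both | 99.2% | 99.9% |
| 1% in both | 96.8% | 99.0% |
| 2% in both | 95.5% | 96.9% |
| 3% in both | 95.5% | 96.2% |

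**Disagreement with Fisher's test.** With an expected count below 5, the Wald interval excludes zero while p ≥ 0.05 in three tables (and their mirror images): 4 vs 0 (p = 0.123), 5 vs 0 (0.43 to 5.82 points; p = 0.061) and 7 vs 1 (0.35 to 7.15; p = 0.067). For surgery, where Fisher's test always applies, it also happens at higher counts: 9 vs 2 (0.41 to 8.34; p = 0.061) and 10 vs 3 (0.08 to 8.67; p = 0.086). The reverse conflict did not occur in any table examined (0 to 59 events per arm). The chance of a conflicting table is 2.5–3.2% at equal rates of 1–3%, 11.5% at 1% vs 3%, 14.3% at 0.5% vs 2% and 29.5% at 0% vs 2%.

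**What a score interval does not repair.** Newcombe still excludes zero at 5 vs 0 (0.18 to 7.11) and 7 vs 1 (0.14 to 8.16). Miettinen-Nurminen does so even at 4 vs 0 (0.12 to 6.26). Over all tables with up to 40 events per arm, one direction counted, the conflicts number 31 for Wald, 29 for Miettinen-Nurminen and 25 for Newcombe.

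**The case against.** The case for leaving the text alone has four parts.

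1. **Consequence.** SAP 7.3.4 says that no p-value outside the primary and key secondary sequence will count as statistically significant. For surgery the protocol specifies only the log-rank comparison, which the SAP keeps, and the counts are reported, so a sparse table would be visible. This stands, and it makes the point minor. It does not make an interval with 80–87% coverage acceptable, and the SAP 7.3.4 statement concerns p-values, not intervals.

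2. **Rates.** Nothing in the documents supports near-zero surgery rates. Protocol 1.1 calls surgery an option for roughly 20% to 50% of those who fail conservative treatment, and Protocol 1.2.3 makes such patients the target population. That is not an expected incidence in the trial, but it does mean that the severe undercoverage is conditional. This stands.

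3. **Scope.** A reader might infer that every Wald interval in the section is wrong. The documents do not support that. The low-count rule needs fewer than 10 events or non-events in 320, which is unlikely for PGIC/CGIC, 30%/50% improvement or composite response. At 5% vs 10%, coverage is already 95.0%. The realistic cases are surgery and perhaps a sparse neurologic category. A reader might also infer that the SAP switches tests for surgery because it saw the approximation fail there; the surgery item contains no switch.

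4. **Remedy.** A reader might expect a score interval to remove the contradiction with the test. It does not. Much of the conflict comes from pairing a near-nominal interval with a conservative exact test. This stands and limits what the fix can claim.

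**Conclusion.** The point holds in a narrow form. In sparse tables the prespecified interval for the difference is not a 95% interval: it loses roughly 8 to 15 points of coverage when rates are very low and unequal with one arm at or near zero, and collapses to zero width with no events. The loss is only 1 to 2 points for 0.5% vs 2%, 1% vs 4% and 2% vs 5%, and there is essentially none at equal low rates or at 5% vs 10%. Every conflict found with Fisher's test has the interval showing a difference that the test does not.

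These figures rest on 160 evaluable subjects per arm and on assumed event rates. No primary or key secondary conclusion depends on the intervals. The Wald interval is a defined, prespecified method that contradicts nothing in the protocol, so this is a cheap improvement of minor severity. A reader might infer a threat to the trial's confirmatory claims; the place of these endpoints outside the gatekeeping sequence rules that out.

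**What to change.** In SAP 7.3.3.3, before unblinding:

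- For post-treatment surgery, and for any other endpoint with a planned interval whenever the low-count rule moves the test to Fisher's, replace the Wald interval with the Newcombe interval built from Wilson score limits. Its coverage is about 95.5–99.9% over the assumed rates, and it gives ±2.3 points at 0 vs 0. Name Newcombe specifically, since Miettinen-Nurminen still excludes zero at 4 vs 0.
- Add one sentence on how a disagreement between Fisher's test and the interval will be read, because some will remain (5 vs 0 and 7 vs 1, for example).
- In the surgery item, replace the word responders, which looks carried over from the neighbouring items.

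The Wald interval can stay where the low-count rule does not apply, except for surgery. The cost is a short edit and one software option, with slightly wider intervals at low counts. No new data are needed, and sample size and error control are unaffected.

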7.3.3.4 Composite responder

A composite responder is a subject who meets all 4 criteria below (A, B, C, and D) as assessed at Week 13:

- a. A reduction of $\geq 30\%$ in worst leg pain score during the past 24 hours assessed by VAS from baseline to Week 13;
- b. Improvement of $\geq 30\%$ in ODI score from baseline to Week 13;
- c. Maintenance or improvement of neurologic status (motor, sensory, reflexes) from baseline to Week 13; and
- d. No "Treatment Failure"

“Treatment Failure” is defined as a subject to whom any of the conditions shown below become applicable until Week 13 after investigational product injection:

- i. Use of additional medication/therapy to treat treatment-emergent adverse events (TEAEs) or complications associated with LDH
 - New prohibited medications used for more than 7 days;
 - Increase of restricted medications used for more than 7 days;
 - Use of new prohibited therapies; or
 - Increase in frequency or intensity of restricted therapies.
- ii. Poor response to investigational product that leads the investigator to judge it necessary to perform a surgical intervention for back pain/leg pain or withdraw from the study
- iii. Increase of measurement value on either vertebral body angle formed by flexion or vertebral body translation from baseline to values:
 - Vertebral body angle formed by flexion of $\geq 5^\circ$, or
 - Vertebral body translation of ≥ 3 mm
- iv. Occurrence of treatment related AEs that lead the investigator to judge it necessary for the subject to have surgical intervention or withdraw from the study

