6.6.2 Restricted Concomitant Medications

Subjects who had been taking restricted concomitant medications to treat LDH at stable dose and regimen for at least 7 days prior to randomization may be enrolled in the study. These restricted concomitant medications include NSAIDs, acetaminophen, muscle relaxants, medicines for neuropathic pain (e.g., pregabalin, gabapentin), and medicines for depression used to treat LDH. Medications stated as restricted concomitant medications for purpose of use other than to treat LDH should also remain in stable dose.

Throughout the follow-up period, subjects are allowed to reduce the amount of their restricted medication drug after injection by consultation with investigators, but they must not add a medication or increase a dose once it is decreased.

All restricted concomitant medications used on an as-needed basis (except for rescue medications) are prohibited.

For further details, see medication listings that will be separately distributed.

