6.7.2 Restricted Concomitant Therapies

Subjects who had been receiving physical therapy (e.g., exercise therapy, thermotherapy, braces, acupuncture, manipulative treatment, transcutaneous electrical nerve stimulation) to treat LDH beginning 7 days or more prior to randomization may continue with that therapy during the study only if the frequency and intensity will not be changed. Subjects are allowed to reduce the frequency or intensity after injection by consultation with investigators, but they must not add new therapy or increase a frequency or intensity once it is reduced.

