8.1.3 Other Secondary

The other secondary efficacy endpoints for this study are as follows:

- Change from baseline in worst leg pain score at each time point
- Change from baseline in worst low back pain score at each time point
- Change from baseline in ODI score at each time point
- Percentage of subjects with negative SLR test
- Percentage of subjects without hypoesthesia, muscle weakness or hyporeflexia
- Patient Global Impression of Change (PGIC) score at each time point
- Clinical Global Impression of Change (CGIC) score at each time point
- Change from baseline in 36-item Short Form Health Survey (SF-36) scores at each time point
- EuroQol Group 5-Dimension Quality of Life instrument, 5-level version (EQ-5D-5L) quality of life (QOL) score and VAS score at Week 13 and Week 52
- Work Productivity and Activity Impairment Questionnaire (WPAI) score at Week 13 and Week 52
- Incidence and amount of rescue medication use over 13 weeks
- Change from baseline in amount of rescue medication use at each time point
- Cumulative distribution of percentage change from baseline in worst leg pain score at Week 13 and Week 52

- Cumulative distribution of percentage change from baseline in ODI score at Week 13 and Week 52
- Responder rate by composite definition^{*1} at Week 13
- Change from baseline in intervertebral disc volume at Week 13 and Week 52
- Change from baseline in herniation volume at Week 13 and Week 52
- Incidence of post-treatment surgery for LDH at the same level of investigational product injection
- Number of subjects with recurrence of LDH^{*2} at Week 52

*1 A subject who meets all 4 criteria below (A, B, C, and D) as assessed at Week 13:

- A. A reduction of 30% in worst leg pain score during the past 24 hours assessed by VAS from baseline to Week 13;
- B. Improvement of 30% in ODI score from baseline to Week 13;
- C. Maintenance or improvement of neurologic status (motor, sensory, reflexes) from baseline to Week 13; and
- D. No “Treatment Failure”

“Treatment Failure” is defined as a subject to whom any of the conditions shown below become applicable until Week 13 after investigational product injection:

- i. Use of additional medication/therapy to treat TEAEs or complications associated with LDH
 - New prohibited medications used for more than 7 days;
 - Increase of restricted medications used for more than 7 days;
 - Use of new prohibited therapies; or
 - Increase in frequency or intensity of restricted therapies.

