7.3.2.1 Data Handling of Worst Leg Pain

The mean worst leg pain score from 7 consecutive days prior to each visit will be targeted as the worst leg pain score for each time point; (the day of the visit itself will not be included but will serve as the anchor). If less than 3 days of worst leg pain scores are available in the day interval prior to a visit, alternative 7-day intervals within the protocol-specified visit window will be examined. Finally, for the Week 52 visit only, if the actual visit day falls outside of the protocol-defined window, intervals in that window will be targeted first. Note that post-baseline visits were scheduled per the protocol with the injection date as day 1; in rare instances, this may be after the randomization date. For the purposes of the below algorithm, the injection date is considered to be day 1.

To calculate the 7-day average, first the worst leg pain score on any of the following days will be eliminated:

- Days after prohibited concomitant therapies of lumbar operation, lumbar percutaneous nucleotomy, or lumbar intradiscal therapies occurred, and
- Days before the previous visit (for example, the Week 2 visit may fall just 5 days after Week 1; thus, the days prior to the Week 1 visit will not be considered as eligible for inclusion in the 7-day Week 2 average).

Anchored by the visit date, the average of the consecutive days prior to each visit will be calculated. If less than 3 days of worst leg pain scores are available of the 7 consecutive days prior to a visit, the following approach will be utilized:

1. Using the visit target day, each day that would fall within the protocol-defined visit window will be identified as the anchor.
2. For each of those days, the corresponding 7 day interval anchored to that end date will be examined and all intervals with a valid average with at least 3 days of data will be identified
3. The interval with the anchor day that falls closest to the visit target day will be selected for the average. In the case of two equidistant valid intervals, the one with the later anchor day will be used.

If an in-person visit is missing altogether, the above process will be used with the corresponding visit target day. If no valid interval can be identified, worst leg pain score will be handled as missing at the time point.

Finally, for the Week 52 visit, if the actual visit day falls outside of the protocol-defined window, the following approach will be utilized:

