7.3.2.2 Sensitivity analyses

As a sensitivity analysis, missing data for participants in the mITT population will be imputed via MI. Twenty repeats of the imputation will be performed using Markov Chain Monte Carlo (MCMC) assuming non-monotone missing. Where the subject was discontinued due to lack of efficacy, due to an AE (with the exception of COVID-19), the subject has met the criteria for treatment failure as described in Section 7.3.3.4, or the subject's values are censored due to a prohibited therapy as described in Section 7.3.2.1, missing values will be imputed drawing from the baseline values, conditioned on the non-missing post-baseline values, of all participants in the mITT population under the assumption that they are missing not at random (MNAR); duration of leg pain will be included as a covariate.

If the study medication was discontinued for any other reason, values will be imputed within treatment group using MI under the assumption that they are missing at random (MAR) with covariates for duration of leg pain, and the weekly average worst leg pain score recorded at each time point (including baseline). The MAR approach will also be applied for sporadic missing values (prior to discontinuation). Values missing due to COVID-19, whether the result of early termination or sporadic missing values, are assumed MAR and unrelated to the endpoint of the weekly average VAS worst leg pain.

Data will be imputed for the full set of visits as described above and the same output will be used as a sensitivity for both the primary at Week 13 and the secondary endpoint at Week 52.

The MMRM analysis as described for the primary will be repeated for each of the 20 sets of data and combined using SAS PROC MIANALYZE. See Appendix [13.2](#) for the list of random seeds.

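### The composite responder rule tolerates up to 7 days of prohibited medication, as long as the Week 13 pain window itself, so a score recorded wholly under a prohibited opioid can still count as a response

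*SAP*

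**What the plan says.** SAP 7.3.3.4 requires a composite responder to meet criteria A to C at Week 13 (pain, ODI, neurologic status) and, as criterion D, to have no Treatment Failure. Limb (i) of Treatment Failure opens with "Use of additional medication/therapy to treat treatment-emergent adverse events (TEAEs) or complications associated with LDH". It has four bullets:

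- "New prohibited medications used for more than 7 days"
- "Increase of restricted medications used for more than 7 days" (the same words stand in protocol 8.1.3 and the SAP)
- use of a new prohibited therapy
- "Increase in frequency or intensity of restricted therapies"

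SAP 7.3.2.1 defines the score behind criterion A: "The mean worst leg pain score from 7 consecutive days prior to each visit will be targeted". The visit day is left out and at least 3 scores are needed. The only treatment-related days removed are those after a lumbar operation, percutaneous nucleotomy or intradiscal therapy. SAP 7.3.1 gives no special handling to any other intercurrent event.

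Protocol 6.6.1 prohibits opioids except as described for rescue in 6.6.4. Section 6.6.4 in turn bars rescue hydrocodone/acetaminophen in the 7 days before the Week 13 visit. For restricted treatment, protocol 6.6.2 says of subjects that "they must not add a medication or increase a dose once it is decreased", and 6.7.2 that "they must not add new therapy or increase a frequency or intensity once it is reduced". The Treatment Failure definition is used once more, in SAP 7.3.2.2, where a missing value is imputed from the baseline distribution if "the subject has met the criteria for treatment failure as described in Section 7.3.3.4".

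**The concern.** Criterion D is the only part of the composite that takes account of added treatment. Its purpose is to stop a subject from qualifying on pain relief that came from something other than the injection. A tolerance for short use does little harm if the use falls well away from the assessment. Here the tolerated length equals the length of the assessment window, so the use that most directly affects the Week 13 score is the use that the rule can miss.

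A second, smaller question is whether starting a restricted drug or therapy counts as an *increase*. The protocol names adding and increasing separately, but the failure bullets name only increasing. Two programmers could classify the same subject differently.

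At stake is the reading of the Week 13 composite response rate in each arm and of the difference between arms.

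**Working it through.** **Inputs.** Failure threshold for prohibited medication: more than 7 days (SAP 7.3.3.4, protocol 8.1.3). Scoring window: 7 days before the visit, minimum 3 scores (SAP 7.3.2.1). Rescue opioid: at most 4 tablets a day, 28 per prescription, 60 in total (protocol 6.6.4). Arm size: 160 (SAP 2.6).

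**Step 1: the rule applied to days of use.** The days are taken as lying inside the 7-day window, except the eighth.

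| Days of prohibited opioid | Failure under limb (i)? | Can cover every scored day? |
|---|---|---|
| 3 | no (3 is not > 7) | yes, if only those 3 days have diary entries |
| 5 | no | yes, if only those 5 days have entries |
| 6 | no | yes, if only those 6 days have entries |
| 7 | no | yes, with a full diary |
| 8 | yes | yes |

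Example: visit on Day 92, opioid on Days 85 to 91. That is 91 - 85 + 1 = 7 days, so limb (i) is not met, yet all seven scores in the average were recorded under the opioid. Changing the threshold to 7 days or more would catch this record but would still pass 3 to 6 days. Only a rule tied to the scored days, or an any-use rule, closes the gap.

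**Step 2: other rules that might catch the subject.**

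- Diary elimination (SAP 7.3.2.1) covers surgical and intradiscal events only.
- A positive opioid test leads to withdrawal (protocol 5.1). After randomization, however, urine tests are done only in subjects receiving or prescribed hydrocodone rescue (protocol Table 1 footnote l and 9.2.7).
- The investigator records Treatment Failure with a reason (protocol 9.5.10), but by the definition in 8.1.3, which has the same threshold.
- The per-protocol repeat covers the primary and key secondary analyses (SAP 7.3.2.3), not the composite.

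**Step 3: rescue hydrocodone.** Supply permits the pattern: 28 / 4 = 7 days from one prescription, and 60 / 4 = 15 days over the study. Section 6.6.1 exempts rescue use from the prohibited list, while 6.6.4 prohibits it in this window. The documents do not say whether such use is a prohibited medication for limb (i).

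**Step 4: the plan's own figure.** The documents give no rate, power or sample size for the composite. The primary sample size reproduces: n = 2 × (1.960 + 1.282)² × 30² / 12² = 131.3, so 132 per arm (133 with the t distribution). Then 133 / 0.85 = 156.5, so 157 per arm and 314 in total, against about 320 planned.

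**Step 5: illustration only; every rate is assumed.** Power = Φ[(d - 1.96 × SE0) / SE1], with SE0 pooled, SE1 unpooled and 160 per arm. For 50% v 35%: d = 0.15, SE0 = 0.0553, SE1 = 0.0546, power 0.78. False responders are then added to each arm.

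| Added, SI-6603 / control | Observed rates | Difference | Power |
|---|---|---|---|
| none | 50% v 35% | 15 points | 0.78 |
| 2% / 2% | 52% v 37% | 15 points | 0.77 |
| 2% / 5% | 52% v 40% | 12 points | 0.58 |
| 2% / 10% | 52% v 45% | 7 points | 0.24 |
| 5% / 2% | 55% v 37% | 18 points | 0.90 |

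The sign of the bias follows the arm with more unscored use.

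**The case against.** The strongest defence is that the case is narrow and visible. The bullet does not require the days to be consecutive, so on a cumulative count a subject with 7 scored days under an opioid becomes a failure with one further day of use before Week 13. Withdrawal for poor response falls under limb (ii), and withdrawal for a treatment-related adverse event under limb (iv). Protocol 5.1 lets the investigator withdraw a subject whose deviations would confound efficacy. SAP 6.2 summarizes and lists prohibited and restricted medication. A short tolerance also fits an estimand that analyses data as observed. All of this limits how often the gap matters. None of it changes the classification of a subject whose use stays within the window and who is not withdrawn. Nor is the scoring-window limit alien to the plan: the protocol already keeps even permitted rescue opioid out of those 7 days.

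A reader might infer three stronger things that the documents do not support.

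- *That added restricted drugs or therapies definitely pass.* The opening line of limb (i) speaks of additional treatment, and starting from none can be read as an increase. The text is ambiguous.
- *That sham gains more false responders, so the difference shrinks.* Limb (i) also covers treatment of adverse events, and protocol 1.2.1.2 names back pain as the most frequent treatment-related event in earlier studies. Subjects on SI-6603 could add more analgesic, which would enlarge the difference.
- *That the sensitivity analysis of the primary endpoint is materially affected.* A composite responder has observed Week 13 pain and ODI, so no Week 13 value is imputed for that subject. Only missing values at other visits could be reclassified.

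**Conclusion.** The gap is certain on the text for prohibited medication. Use on 3 to 7 days that covers every scored day is not Treatment Failure under limb (i), and no rule removes those scores. Whether the subject then counts as a responder is conditional: criteria A to C must be met and limbs (ii) to (iv) must not apply.

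The size is unknown. The illustration shows only that a few points of unequal misclassification can move the composite difference either way, and it rests wholly on assumed rates. The endpoint is supportive and lies outside the testing sequence in SAP 7.3.4, so no confirmatory conclusion depends on it. The add-versus-increase point is a clarification. A rule that any corticosteroid injection is a failure would be a stricter endpoint by preference, and nothing in the documents requires it. The scoring-window change is worth making because it is cheap and the present rule misclassifies an identifiable subject.

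**What to change.** Make these changes in SAP 7.3.3.4 before unblinding, with matching text for protocol 8.1.3. They concern endpoint classification only and alter no rule on treatment.

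1. Keep the present threshold and add that prohibited-medication use on any day contributing to the Week 13 leg-pain average counts as Treatment Failure (or as non-response at Week 13). Refer to the interval actually selected under SAP 7.3.2.1, since a fallback interval may be used. Derive it from the dated medication records (protocol 9.4.1) and the daily diary.
2. State whether rescue hydrocodone taken in that window counts, and reconcile protocol 6.6.1 with 6.6.4 on this point.
3. State that an increase of restricted medication or therapy includes additions, in line with the opening of limb (i) and with protocol 6.6.2 and 6.7.2, and that the post-injection allowance in 6.6.3 is respected.
4. Use the same definition in SAP 7.3.2.2, and note that it acts there only on missing values.

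The cost is a wording change and some programming on data already collected. Composite response rates may be slightly lower.
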